3.1.3 Study Endpoints

3.1.3.1 Stage I

3.1.3.1.1 Efficacy Endpoints

Primary Efficacy Endpoint:

Time to resolution of hypoxia (Time frame: Up to 28 days)

This endpoint will be considered to have been met when the patient has attained a score of 4 or lower on the 10-point ordinal scale of clinical status and either of a) or b), and c) is met:

- a) Score is ≤ 4 on consecutive assessments over the next 5 days, if patient continues to remain in hospital (i.e., has not been discharged).

OR

- b) Patient was discharged before five consecutive assessments (after reaching a score of 4).

AND

- c) The patient has survived and has not been re-admitted to hospital for COVID-19 management through Day 28.

Secondary Efficacy Endpoints:

1. Time to discharge from hospital
2. Time (no. of days) from randomization to the earliest time when **ALL** COVID-19 associated symptoms (fever, chills, cough, sore throat, malaise, headache, muscle pain, gastrointestinal symptoms – specifically diarrhoea and vomiting, shortness of breath or dyspnoea) are scored by the Investigator/trained study personnel as either '0=absent' or 'mild =1' in assessments over a period of 24 hours, when assessed from baseline to Day 28 or discharge from hospital (if discharge happens earlier than Day 28).
3. Percentage of patients with score of either '0=absent' or 'mild =1' over a period of 24 hours, for **ALL** COVID-19 associated symptoms, by Days 4, 7, 10, 14, 21 and 28 or discharge (if discharge happens earlier than one or more of the above-mentioned timepoints)

Note: *Symptoms evaluated are fever, chills, cough, sore throat, malaise, headache, muscle pain, gastrointestinal symptoms- specifically, diarrhoea and vomiting, shortness of breath or dyspnoea. The Investigator/trained study personnel will assess (including by enquiry with the patient, as*

Study code: NV-05-983-2020
 Protocol No.: CVD-04-CD-001
 Sponsor name: [name], Limited
 Clinical Study Protocol

necessary) and score the severity of each COVID-19 associated symptom on a 5-point Likert-type scale (0= absent, 1= mild, 2=moderate, 3= severe, 4= very severe/critical).

4. Time to improvement in **EACH** of the symptoms of fever, chills, cough, sore throat, malaise, headache, muscle pain, gastrointestinal symptoms- specifically diarrhoea and vomiting, shortness of breath or dyspnoea by at least 1 grade over baseline.

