5.1.12 Rescue Medications

Acute deterioration of disease conditions has been reported in some COVID-19 patients. In such cases, further treatment management will be as per the Principal Investigator's or a medically qualified Sub-Investigator's discretion and hospital protocol or practice for treating COVID-19.

Study treatment with the IMPs (Favipiravir/Placebo) will be permanently discontinued before starting treatment with convalescent plasma. In such cases, the Principal Investigator or a Sub-Investigator will record assessment specified in [Section 6.3.1.5](#) in accordance with [Section 3.1.6.2.2](#).

Study treatment with the IMPs can be continued with rescue treatment like remdesivir, and IL-6 pathway antagonists like tocilizumab. The details of rescue medication (medication, dose, route, start date, frequency of administration, end date etc.) will be captured.

The use of low molecular weight heparin, vasopressors, rehydration fluids is allowed as per patient's clinical status and local management guidelines/hospital practice.

Study code: NV-05-983-2020
Protocol No.: CVD-04-CD-001
Sponsor name: [name], Limited
Clinical Study Protocol

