- 277 – Respiratory failure (i.e., need for mechanical ventilation, ECMO, noninvasive
 278 ventilation, or high-flow nasal cannula oxygen delivery)
- 279
- 280 – Need for invasive mechanical ventilation
- 281
- 282 – Need for intensive care unit (ICU) level care based on clear definitions and specific
 283 clinical criteria
- 284
- 285 – Need for hospitalization based on clear definitions and specific clinical criteria
- 286
- 287 – Objective measures of sustained improvement (e.g., return to room air or baseline
 288 oxygen requirement)
 289

²² See the guidance for industry *Adaptive Design Clinical Trials for Drugs and Biologics* (November 2019).

Contains Nonbinding Recommendations

- 290 – Sustained clinical recovery (e.g., resolution of symptoms)
 291
- 292 • The choice, time frame, and interpretation of endpoints may differ depending on the
 293 population evaluated in the trial. For example,
 294
 - 295 – In a trial in severe and/or critical patients, examples of appropriate endpoints could be
 296
 - 297 ▪ All-cause mortality at an appropriate time point (e.g., at least 28 days)
 298
 - 299 ▪ Proportion of patients alive and free of respiratory failure at an appropriate time
 300 point (e.g., at least 28 days)
 301
 - 302 ▪ Clinical status at an appropriate time point assessed using an ordinal scale²³ that
 303 incorporates multiple clinical outcomes of interest (e.g., death, mechanical
 304 ventilation) ordered by their clinical importance²⁴
 305
 - 306 ▪ Time to sustained recovery assessed over an appropriate duration
 307
 - 308 – In an outpatient treatment trial, examples of appropriate endpoints could be
 309
 - 310 ▪ Proportion of patients hospitalized by an appropriate time point (e.g., at least 28
 311 days)
 312
 - 313 ▪ Time to sustained clinical recovery assessed over an appropriate duration
 314
 - 315 • Sponsors should address potential relapses in their endpoint definitions to ensure
 316 adequate assessment of the durability of response.
 317
 - 318 • In phase 2 treatment trials, a virologic measure may be acceptable as a primary endpoint
 319 to support a phase 3 clinical endpoint study. However, virologic endpoints are not
 320 appropriate as primary endpoints in a phase 3 trial because there is no established
 321 predictive relationship between magnitude and timing of viral reductions and the extent
 322 of clinical benefit of how a patient feels, functions, or survives. Additionally, the optimal

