10.6 Efficacy Analysis

10.6.1 Primary Efficacy endpoint

Primary Efficacy endpoint will be as follows:

1. Time to resolution of hypoxia

The primary efficacy endpoint is “Time to resolution of hypoxia (Time frame: Up to 28 days)”

This endpoint will be considered to have been met when the patient has attained a score of 4 or lower on the 10-point ordinal scale of clinical status and either of a) or b), (as applicable) and c) is met:

- a) Score is ≤ 4 on consecutive assessments over the next 5 days, if patient continues to remain in hospital (i.e., has not been discharged).

OR

Statistical Analysis Plan
Sponsor: [name], Inc

Study Number: NV-05-983-2020

Version: 2.0 Date: 06JAN2021

- b) Patient was discharged before five consecutive assessments (after reaching a score of 4)

AND

- c) The patient has survived and has not been re-admitted to hospital for COVID-19 management through Day 28.

*Note: Part c) is applicable to patients in both a) and b).
 i.e. Time to resolution of Hypoxia = either "a and c" OR "b and c" is met.*

Time to resolution of hypoxia will be compared between the treatment groups using the Cox proportional hazard model with age, gender, and baseline score on the 10-point ordinal scale of clinical status as covariates. The hazard ratio and its corresponding two-sided 95% confidence interval (CI) and two-sided p -value at 5% level of significance will be obtained from the above Cox proportional hazard model.

As the patients were in the hospital until discharge, missing data in the daily WHO clinical status score were few. To facilitate the definition of the durable response, a very limited and conservative imputation will be implemented to impute a missing clinical status score if adjacent to a valid score on both sides, the imputed score will be the higher (worse) of the two, as discussed in Section 9.5.1.

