Necessary steps will be taken to properly manage the situation of informative censoring for patients who did not reach the resolution of hypoxia endpoint. For censored patients who died of any cause, discontinued or were lost to follow-up due to treatment-related adverse events or lack of efficacy, they will be censored at Day 28. However, censored patients who discontinued or were lost to follow-up for reasons that were independent of the study medication will be censored at the day of discontinuation of lost to follow-up. Censored patients who were still in the study follow-up at the time of the analysis will be censored at the last day of available follow-up data.

The above primary endpoint analysis will be done using ITT population

Also, the primary efficacy analysis will be repeated using PP population.

Sensitivity analysis for primary endpoint [12](#):

Three sensitivity analyses are planned.

1. The first is a more relaxed definition of time to resolution of hypoxia. In this analysis, the resolution of hypoxia is defined if subject's clinical status score ≤ 4 is maintained for two consecutive days. The timing of the resolution event will still be the first day when the score falls to 4 or lower. This sensitivity analysis will be done using ITT as described in the primary endpoint.

Statistical Analysis Plan
Sponsor: [name], Inc

Study Number: NV-05-983-2020

Version: 2.0 Date: 06JAN2021

2. The second sensitivity analysis will be based on Kaplan-Meier estimates and log-rank test. Median time to event, along with standard error, percentage of patients achieved resolution of hypoxia, percentage of patients censored, and two-sided p-value obtained using log-rank test at 5% level of significance will be presented for observed case using ITT population.
3. The third sensitivity analysis will be a worst-rank analysis proposed by Lachin (1999). The two treatment groups will be compared by a Wilcoxon-Mann-Whitney test as implemented in SAS PROC NPAR1WAY. Tied ranks will be assigned the midrank. The ranks will be determined as follows:
 - 1) The lowest (best) ranks will be given to patients who meet the primary endpoint definition of treatment success, beginning with the earliest treatment success after beginning of treatment, and survive to Day 28.

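### Part (c) of the primary endpoint cancels a resolution only for death or re-admission, so a never-discharged inpatient who later returns to oxygen or ventilation still counts as an early resolution

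*SAP*

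**What the plan says.** SAP 10.6.1 defines resolution of hypoxia as a first score of 4 or lower on the WHO 10-point scale plus one of two durability routes:

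- Route (a), for patients still in hospital: "Score is ≤ 4 on consecutive assessments over the next 5 days, if patient continues to remain in hospital (i.e., has not been discharged".
- Route (b): "Patient was discharged before five consecutive assessments (after reaching a score of 4".

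Part (c) applies to both routes: "The patient has survived and has not been re-admitted to hospital for COVID-19 management through Day 28".

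The same rule stands in SAP 8.2 and in Protocol 3.1.3.1.1 and 7.1.1.1, and SAP Appendix I restates it for the interim analysis. On the scale (Protocol Table 3), 5 is conventional oxygen, 6 is high-flow or non-invasive support, and 7 to 9 are mechanical ventilation.

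The worst-rank sensitivity analysis is built on the same event: "The lowest (best) ranks will be given to patients who meet the primary endpoint definition of treatment success".

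The FDA guidance reproduced as Protocol Appendix I says, in its section on efficacy endpoints: "Sponsors should address potential relapses in their endpoint definitions to ensure" adequate assessment of how durable the response is.

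**The concern.** Part (c) looks like a protection through Day 28, but for inpatients it works only through death. After the five-day window, re-admission is the only other cancelling event, and it requires a prior discharge.

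The case is foreseeable. Study drug stops by Day 10 while the endpoint runs to Day 28. Patients may stay in hospital after coming off oxygen: Protocol Table 4 has a category for stays prolonged for infection control, and discharge follows national rules and hospital practice. Protocol 5.1.12 notes that "Acute deterioration of disease conditions has been reported in some COVID-19 patients".

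What is at stake is the meaning of the primary result. SAP 9.5.1 and 10.6.1 describe the endpoint as a durable response, yet a patient ventilated on Day 28 can be reported as resolved in the first week. If such relapses differ between arms, the primary hazard ratio is also biased.

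**Working it through.** **1. Apply the rule to two patients.**

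| | Inpatient throughout | Discharged, then re-admitted |
|---|---|---|
| Score first 4 or lower | Day 4 | Day 4 |
| Durability | 4 on Days 4 to 9: (a) met | Discharged Day 6: (b) met |
| Later course | High-flow oxygen Day 12, ventilated Day 15, alive and ventilated Day 28 | Re-admitted Day 12 for low-flow COVID-19 oxygen, alive Day 28 |
| Part (c) | Survived, never re-admitted: met | Re-admitted: not met |
| Primary outcome | Resolved, Day 4 | Not resolved |

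The patient with the worse course is the success.

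**2. Look for a rule that closes the gap.**

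- SAP 9.3 asks only for a 24-hour evaluation.
- Sensitivity analysis 1 is looser, at two consecutive days.
- Sensitivity analysis 2 (Kaplan-Meier and log-rank) names no other event definition.
- Sensitivity analysis 3 puts everyone who meets the primary definition and survives to Day 28 in rank group 1. Day 28 status orders only group 4, the patients who did not meet it. The inpatient above outranks a patient who never resolved and is on low-flow oxygen at Day 28.

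**3. Reproduce the plan's sample size (SAP 9.6).** Inputs: hazard ratio 1.25, two-sided 0.05, 80% power, event probabilities 0.9 and 0.8, 371 per arm.

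- Schoenfeld: 4 × (1.960 + 0.842)² / (ln 1.25)² = 630.5, so 631 events, as stated.
- 371 × 0.9 + 371 × 0.8 = 630.7 events, in agreement.

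**4. Power if relapse is equal in both arms.** Power = Φ(√E × ln 1.25 / 2 − 1.960).

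- E = 631: Φ(2.803 − 1.960) = 80.0%.
- 5% of events reversed, E = 631 × 0.95 = 599.4: Φ(2.732 − 1.960) = 78.0%.
- At the final level of 0.04521 from SAP Appendix I, the same single-look formula gives 78.8% and 76.7%.

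**5. Effect on the hazard ratio.** The relapse rate is not in the documents, so it is varied. Assumptions: constant hazards, resolution times rounded up to days, control resolution 0.80 by Day 28, and a written-rule hazard ratio of 1.25. This implies favipiravir resolution of 1 − 0.2^1.25 = 0.866. (The plan's 0.9 against 0.8 would imply ln 0.1 / ln 0.2 = 1.43 under constant hazards; 1.25 is kept because it is the stated design effect.) Every relapser is counted as unresolved at Day 28.

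| In-hospital relapse among resolvers, control / favipiravir | Written rule | Relapsers unresolved |
|---|---|---|
| 5% / 5% | 1.25 | about 1.23 |
| 0% / 5% | 1.25 | about 1.12 |
| 5% / 0% | 1.25 | about 1.39 |

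These are simulation results. A direct expected-count calculation with tie correction gives 1.23, 1.11 and 1.38, so the second decimal should not be leaned on. At 371 per arm, 5% relapse reverses about 371 × 0.80 × 0.05 = 15 control events and 371 × 0.866 × 0.05 = 16 favipiravir events.

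**The case against.** The strongest reply is that this is a pre-specified design choice, stated consistently in both documents. How long recovery must last is a judgement, and the appended guidance is non-binding and accepts sustained recovery over an appropriate duration. That is fair for the choice of five days. It does not explain why one relapse cancels the event after discharge but not before it, and the plan's own aim is durability.

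Second, the affected group is narrow. Relapse inside the window fails (a), and relapse followed by death by Day 28 fails (c). What remains is relapse after the window, without discharge, in a survivor. This stands.

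Third, a reader might infer that a late rebound would go unseen. The documents do not support that. The mixed model of change in the 10-point score; the percentage, time and duration analyses of ICU care, high-flow or non-invasive support and ventilation; the Stage II worsening endpoint to Day 60; and the interim progression comparisons would all show it. They do not feed into the primary result, and the Stage I percentages (secondary endpoint 12) are tabulated without a between-arm test.

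Fourth, a reader might infer that the rule flatters favipiravir, or that one arm is sheltered by longer stays. Nothing in the documents gives a direction, and the trial is double-blind.

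Finally, the illustration censors all relapsers, whereas the fix below lets those who recover again count from a later date. The table therefore overstates the shift that the fix would produce in those patients. For example, with 0% against 10% relapse, if half recover again 12 days after first resolution (an assumption), the hazard ratio is about 1.07 rather than about 0.99.

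**Conclusion.** The gap is real and lies in the governing definition. Beyond the five-day window, an inpatient's resolution survives any deterioration short of death by Day 28, while a discharged patient's does not survive re-admission. No planned sensitivity analysis corrects this, and the worst-rank analysis repeats it.

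The size cannot be computed from the documents. If relapse is equal, the effect is small: 5% in each arm moves 1.25 to about 1.23 and power from 80% to about 78%. With a 5-point imbalance the hazard ratio would be about 1.12 or about 1.39, depending on which arm relapses more. These figures rest on the assumptions in step 5 of the check.

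The claims that hold are that the endpoint does not measure what its name says for this group, and that any imbalance would bias the primary result in a direction not knowable in advance. The documents do not support saying that the trial is underpowered for this reason, that relapse would be hidden, or that the result is tilted towards favipiravir.

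**What to change.** In SAP 8.2, 10.6.1 and Appendix I, and in Protocol 3.1.3.1.1 and 7.1.1.1, add a third condition to part (c): besides survival and no COVID-19 re-admission, no later in-hospital 10-point score above 4 through Day 28. Date resolution at the first day of the last unbroken run of scores of 4 or lower, with that run itself meeting (a) or (b). Apply the same rule to rank group 1 of the worst-rank analysis; survivors followed to Day 28 who no longer qualify then fall into group 4.

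Timing matters, because SAP Appendix I plans an unblinded interim on this endpoint at 390 randomized subjects or those enrolled by the end of 2020, and the SAP is dated 06 January 2021. Make the change blinded, before Stage I lock and before any unblinded result on the current rule is known. If the interim has already used the current rule, keep the primary definition, pre-specify the stricter one as a sensitivity analysis, correct the worst-rank rule, and report by arm how many resolvers had a later score above 4.

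Cost: wording and a derivation change, with no new data, since the 10-point score is recorded daily to Day 28 or discharge. The event count falls slightly and some dates move later. A single score of 5 on Day 20 would move a Day 4 resolution to Day 21, so the team should accept that consequence explicitly.

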5.1.1 Method of Assigning Patients to Treatments

A total of 780 eligible patients will be assigned randomly to one of two treatment groups in 1:1 ratio, so as to have approximately 390 patients in favipiravir + supportive care group and 390 patients in placebo + supportive care group. Details of the interim analysis and futility assessment are provided in the Statistical Analysis Plan (SAP) for the Interim Analysis.

Patients will be randomized to the favipiravir + supportive care group or placebo + supportive care group in a 1:1 ratio and a conditional stratification will be performed to include at least 15% of female patients, at least 30% of patients with either category of baseline disease severity (i.e., moderate and severe) and at least 30% of patients aged more than 50 years randomized in each of the treatment groups. If there is an impact on the patient recruitment rate due to limits enforced by the stratification of patients based on the category of baseline disease severity, a decision may be made to waive the stratification based on disease severity. The percentage of stratification may be adjusted according to the re-estimated sample size. The randomization schedule will be generated by CRO statistical team, in SAS, (version 9.4 or higher), according to CRO's standard operating procedures (SOPs).

All patients who sign an IRB/IEC approved informed consent form and authorization for the use and disclosure of protected health information will be assigned a unique patient identity code (PIC) consisting of 03-digit center/site code and three digits (004) patient specific code. The randomization code will be captured separately as an additional identity.

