For the SOLIDARITY trial, a COVID-19 specific ordinal scale has been developed by WHO to assess the clinical status of the patient at baseline and to monitor over time the changes of the clinical status. [Table 3](#) shows the scores assigned on an ordinal level to each status.

Study code: NV-05-983-2020
 Protocol No.: CVD-04-CD-001
 Sponsor name: [name], Limited
 Clinical Study Protocol

Table 3: The 10-point ordinal scale used in the WHO SOLIDARITY trial for assessment of patients' clinical status

Score	Description
0	Uninfected, no viral RNA
1	Asymptomatic, viral RNA detected
2	Symptomatic, independent
3	Symptomatic, Assistance Needed
4	Hospitalized: no oxygen therapy
5	Hospitalized, on oxygen
6	Hospitalized, Oxygen by NIV or high-flow
7	Mechanical ventilation, p/f>150 or s/f >200
8	Mechanical ventilation, p/f<150 or s/f<200 OR vasopressors
9	Mechanical ventilation, p/f<150 AND vasopressors, dialysis, or ECMO
10	Death

Note: Score categories 3,2,1 and 0 apply even if the patient continues to remain in the hospital.

9. Changes over time in patient's clinical status on the 8-point ordinal scale
 - a. Time (no. of days) from randomization to attain clinical status score of 4 or lower
 - b. Proportion of patients in whom clinical status score of 4 or lower has been attained by Days 4, 7, 10, 14, 21 and 28 or discharge (if discharge happens earlier than one or more of the above-mentioned timepoints)
 - c. Time (no. of days) from randomization to attain clinical status score of 3 or lower
 - d. Proportion of patients in whom clinical status score of 3 or lower has been attained by Days 4, 7, 10, 14, 21 and 28 or discharge (if discharge happens earlier than one or more of the above-mentioned timepoints)
 - e. Time (no. of days) from randomization to clinical status score improvement by 1 and by 2 points (from baseline)
 - f. Proportion of patients for whom clinical status score improvement by 1 and by 2 points has been attained by Days 4, 7, 10, 14, 21 and 28 or discharge (if discharge happens earlier than one or more of the above-mentioned timepoints)

The 8-point ordinal scale of Clinical Status is adapted from the one used in the Adaptive COVID-19 Treatment Trial- 1 (ACTT-1) that formed basis of approval for Veklury® (Remdesivir or RDV) in moderate to severe COVID-19 in the United States. [Table 4](#) shows the scores assigned on an ordinal level to each status.

Study code: NV-05-983-2020
 Protocol No.: CVD-04-CD-001
 Sponsor name: [name], Limited

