11.4 Efficacy Analyses

11.4.1 Primary Efficacy Analyses

Analysis of the primary endpoint:

The time from the start of administration of the study drug to time to *resolution of hypoxia* as described in the [Section 3.1.3.1.1](#) will be compared between the treatment groups using the Cox proportional hazard model with age, gender and disease severity (moderate and severe) as factors and baseline WHO ordinal score at the start of administration of the study drug as baseline covariates. The hazard ratio and its corresponding 95% confidence interval (CI) and p-value will be obtained from the above Cox proportional hazard model; Also Median time, Inter quartile range estimate etc. will be presented and Kaplan-Meier plot will be plotted. All the efficacy analysis mentioned will be performed using ITT and PP population.

For censored patients who died of any cause, discontinued or were lost to follow-up due to treatment-related adverse events or lack of efficacy, they will be censored at Day 28. However, censored patients who discontinued or were lost to follow-up for reasons that were independent of the study medication will be censored at the day of discontinuation of lost to follow-up. Censored patients who were still in the study follow-up at the time of the analysis will be censored at the last day of available follow-up data.

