11.4.2 Secondary Efficacy Analyses

All the secondary endpoints will be analysed descriptively and inferentially wherever necessary and more details on statistical analysis will be explained in the SAP. If there is a discrepancy in the planned analysis between the protocol and SAP, the SAP takes precedence.

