This statistical analysis plan (SAP) provides explicit guidance and describes the planned statistical and data handling methods to be followed during the final analyses and reporting of data collected in clinical trial CVD-04-CD-001. The intention of this document is to provide detailed information of the planned analysis of trial data related to safety and efficacy, and to describe applicable statistical procedures explicitly. Relevant statements are quoted directly from the protocol, within the applicable sections in this document (SAP). This SAP should read in conjunction with the study protocol version Final 5.0 dated 06 JAN 2021 and electronic case report form (eCRF) (version Final 3.0 dated 26-NOV-2020).

7 Study Objectives

Primary Objective:

- To evaluate the efficacy of oral favipiravir in improving the time to resolution of hypoxia in moderate to severe COVID-19 patients

Secondary Objectives:

- To evaluate the efficacy of oral favipiravir in improving the clinical and virological outcomes in moderate to severe COVID-19 patients
- To assess the tolerability and safety of favipiravir in the targeted study population

8 Study Design

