10.7.10 Hospitalization

Listing of patients who require oxygen supplementation, ICU admission, Oxygen by HFNC or NIV and Invasive Mechanical Ventilation will be listed.

10.7.11 Subgroup Analysis:

Subgroup analysis will be performed for the “Time to resolution of hypoxia” by considering the severity category (moderate vs severe categories) as a subgroup using ITT population as an observed case analysis.

Subgroup analysis will be performed for the “Time to resolution of hypoxia” by considering the race category (White/ Caucasian vs Non-White / Non-Caucasian) as a subgroup using ITT population as an observed case analysis.

Subgroup analysis will be performed for the “Time to resolution of hypoxia” by considering the age category (Age group <50 years, Age group ≥50 years) as a subgroup using ITT population as an observed case analysis.

Subgroup analysis will be performed for the “Time to resolution of hypoxia” by considering the gender category as a subgroup using ITT population as an observed case analysis.

11 Deviation from the Study Protocol

Not applicable

12 Database Lock and Unblinding

There will be two database lock for this study. One for stage I (Primary) and another one for Stage II (Secondary) analysis. The SAP will be finalized prior to primary database lock. After the data cleaning process is finalized according to the data management plan (DMP) and the assignment of patients to the analysis populations is agreed and signed by the Sponsor, the study database will be locked for primary and secondary separately.

13 References

1. Lachin J. M. (1999). *Worst-Rank Score Analysis with Informatively Missing Observations in Clinical Trials. Controlled Clinical Trials. 20:408–422.*

	Statistical Analysis Plan Sponsor: [name], Inc	
	Study Number: NV-05-983-2020	Version: 2.0 Date: 06JAN2021

14 Appendices

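### The SAP drops disease severity from the protocol's primary Cox model, at both the interim and final analyses, and records no deviation; power is lost if severity is prognostic beyond the baseline score.

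*SAP*

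**What the plan says.** Protocol 11.4.1 compares the arms by a Cox model "with age, gender and disease severity (moderate and severe) as factors and baseline WHO ordinal score" as a covariate. SAP 10.6.1 uses a "Cox proportional hazard model with age, gender, and baseline score on the 10-point ordinal scale of clinical status as covariates", and SAP Appendix I repeats that covariate list for the unblinded interim.

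The protocol settles which model governs: "If there is a discrepancy in the planned analysis between the protocol and SAP, the SAP takes precedence". Its section 1.5.3 expects changes to the planned analysis to be documented in an amendment, in the SAP, or in both. SAP section 11, headed "Deviation from the Study Protocol", says only that it does not apply.

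The SAP is version 2.0 of 06JAN2021 and states: "This SAP should read in conjunction with the study protocol version Final 5.0 dated 06 JAN 2021".

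Severity appears elsewhere in two ways. Protocol 5.1.1 sets a minimum share of 30% for each severity category, although "a decision may be made to waive the stratification based on disease severity". SAP 10.7.11 analyses the primary endpoint "by considering the severity category (moderate vs severe categories) as a subgroup using ITT population".

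**The concern.** The covariate set of a confirmatory primary analysis differs between the two governing documents, and the section meant to record such differences says there are none. A reader cannot tell when or why severity was removed. The timing makes this matter more: the interim is unblinded, and its cut-off falls close to the SAP date.

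The statistical stake is power. The Cox hazard ratio is not collapsible: when a prognostic covariate is left out and the drug works, the estimated treatment hazard ratio moves toward 1 even in a perfectly balanced trial. The size of the effect depends on how much severity predicts once the baseline score is in the model.

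**Working it through.** **1. The models side by side**

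| Term | Protocol 11.4.1 | SAP 10.6.1 (final) | SAP Appendix I (interim) |
|---|---|---|---|
| Age | yes | yes | yes |
| Gender | yes | yes | yes |
| Baseline 10-point score | yes | yes | yes |
| Disease severity | yes | **no** | **no** |

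**2. Whether the score replaces severity**

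Protocol 4.1.1 defines moderate disease by SpO2 of 94% and severe disease by SpO2 of 93% or below, or PaO2/FiO2 below 300. In Protocol Table 3, score 5 is "Hospitalized, on oxygen" whatever the saturation. Entry requires a score above 4 and candidates for intubation are excluded, so baseline scores are largely limited to 5 and 6. Moderate and severe patients can share a 5.

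**3. Whether another planned analysis adjusts for severity**

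The three sensitivity analyses in SAP 10.6.1 are a relaxed endpoint definition, a log-rank test and a worst-rank Wilcoxon test. None adjusts for severity. The subgroup analysis gives results within each category, not a severity-adjusted overall estimate.

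**4. The plan's own figures**

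- Events (Schoenfeld, two-sided 0.05, 80% power, hazard ratio 1.25): 4(1.960 + 0.842)² / (ln 1.25)² gives 631, as stated.
- Patients: 631 / 0.85 = 742.4, or 371 per arm, as stated.
- Power at the final threshold Z = 2.0027: Φ(ln 1.25 × √631 / 2 − 2.0027) = Φ(2.803 − 2.003) = 78.8%.

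The trial is therefore already slightly under 80% before any covariate is dropped.

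**5. Cost of omission, by simulation**

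The same simulated data were fitted with and without severity; age, gender and score were in both models. There were 742 patients, a true hazard ratio of 1.25, exponential times rounded up to days, 80% control events by Day 28, no dropout, success at Z ≥ 2.0027, and 4000 replicates. About 615 events result rather than 631, because 80% in control with a hazard ratio of 1.25 implies 1 − 0.2^1.25 = 86.6% on favipiravir, not the plan's 90%.

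Assumed, because the documents do not say: half the patients severe; score 6 in 5% of moderate and 20% of severe patients, with half the hazard of score 5; an age effect of 0.86 per SD; no sex effect. The severity effect is the hazard of resolution in moderate versus severe patients at the same score.

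| Assumed severity effect | Power without severity | Power with severity | Loss, points (95% simulation error) |
|---|---|---|---|
| 1.0 | 78.4% | 78.3% | none |
| 1.25 | 75.9% | 76.5% | 0.7 (±0.5) |
| 1.5 | 75.3% | 76.9% | 1.6 (±0.7) |
| 2.0 | 72.1% | 78.3% | 6.1 (±1.0) |
| 3.0 | 62.7% | 77.5% | 14.8 (±1.3) |

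Losses are paired differences, so they can differ by 0.1 from the rounded columns. The estimated treatment hazard ratio without severity is 1.23 at an effect of 2.0 and 1.21 at 3.0, against 1.25 with severity. With 30% to 70% severe, the loss is 1.5 to 1.9 points at 1.5 and 5.0 to 6.1 points at 2.0. Under the null with a severity effect of 2.0, two-sided type I error is 4.2% without severity and 4.5% with it.

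**6. Cross-check**

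A simpler simulation used 742 patients, a mean event probability of 0.85, threshold 1.96, score 6 only in 20% of severe patients, no age or sex terms, and 2500 replicates. Across 30%, 50% and 70% severe, the losses were nil at 1.0, under 1 point at 1.25, 1.8 to 2.9 points at 1.5, 3.6 to 6.6 at 2.0, and 11.4 to 15.7 at 3.0. Direction and rough size agree.

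**The case against.** The governing model is not in doubt. The SAP states one explicit model, the same at interim and final, and the protocol gives the SAP precedence. No choice is left until after unblinding. That stands, but precedence decides which model runs; it does not make the statement in SAP section 11 true.

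A reason may exist out of sight. The copies read lack their front pages, where a revision history might sit, and the visible protocol text does not confirm that it is version 5.0. This limits what can be said about the absence of any explanation. It does not alter the visible section 11.

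The power loss rests on assumption. The documents give no prognostic effect for severity, no severity mix beyond the 30% minimum and no score distribution. Moderate and severe can differ by one percentage point of SpO2 at a single reading, so the added information may be small. This stands in full: effects of 2.0 and 3.0 are illustrations, and nothing in the documents supports them as likely.

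The retained score is itself a measure of severity, and a severity subgroup is planned. Both are true, but the score cannot separate the two categories among patients on standard oxygen. The regulatory guidance appended to the protocol, which is nonbinding, names baseline severity among covariates to consider and says the primary analysis should be prespecified in the protocol.

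Finally, if the interim has been run, restoring severity to the primary model could be worse than leaving it out. That is correct, and the remedy allows for it.

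**Conclusion.** The concern holds. The primary model differs from the protocol's by one covariate, at both analyses, and SAP section 11 wrongly records no deviation. That part rests on the text alone, provided the protocol read is the version the SAP cites.

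The consequence for power is conditional: nil if severity adds nothing beyond the score, about 2 to 3 points at an assumed severity effect of 1.5, about 4 to 7 at 2.0, and about 11 to 16 at 3.0. Type I error is not inflated. Keeping severity costs essentially nothing if it proves uninformative (78.3% versus 78.4% power). The point should be corrected, but it does not threaten the validity of the trial.

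**What to change.** - **If the interim has not been unblinded:** restore baseline disease severity (moderate or severe) as a factor in the Cox models of SAP 10.6.1 and Appendix I, matching Protocol 11.4.1. Keep it even if the severity quota is waived. The cost is one covariate already collected, plus SAP wording.
- **If the unblinded interim has already been run with the reduced model:** keep that model as primary so that the final analysis matches the one used at the interim boundary. Declare and justify the departure from Protocol 11.4.1 in SAP section 11, and pre-specify a severity-adjusted Cox analysis of the primary endpoint as a fourth sensitivity analysis. The cost is one paragraph and one extra model.

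The second case is a real possibility. The interim was due on the first 390 randomized subjects or on those enrolled by the end of 2020, whichever came first, and the SAP is dated 06JAN2021. The SAP should state which case applies.
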